Safety Follow-up Population: The safety follow-up population is defined as patients in the safety population who entered the follow-up period and who did not discontinue in the follow-up period for the reason 'Lost to Follow-up'.

6.1.4. *Handling of X-ray Data*

X-rays are scheduled at the following visits: Screening (Visit 1), Week 16 (Visit 9), Week 24 (Visit 11), and Week 52 (Visit 15). X-rays are obtained at an early termination only if the most recent x-ray was more than 12 weeks ago.

There may be instances in which the x-rays are obtained on a date different from the scheduled InForm visit date. Also, there may be instances in which the set of x-rays for a visit (2 hands/wrists, 2 feet) are split across dates, resulting from the need to re-acquire some images in the set. To maximize the use of the observed data and avoid imputation, the following rules will be applied in the analysis:

1. Postbaseline x-rays administered within 14 days prior to the scheduled InForm visit date, or within 30 days after the scheduled InForm visit date, will be associated with that respective InForm visit for analysis.
2. An x-ray set split across different dates will have the data combined as long as the images are collected within 30 days of each other. The earlier x-ray date will be considered to be the date of the x-ray set.

Any linear extrapolation will be based on the date of the x-ray set instead of the InForm visit date.

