6.3.2. Missing Data Imputation for the Structural Progression Endpoint (van der Heijde mTSS)

1. Primary method: Linear extrapolation method

The primary approach to the analysis of the structural progression data will be the linear extrapolation method, which assumes that individual patients would continue to accrue structural damage in their joints at the same rate that was observed at their time of last observation. The linear extrapolation method has been established as an appropriate missing data imputation method in other Phase 3 RA trials (Keystone et al. 2004, 2008, 2009; Cohen et al. 2006; Smolen et al. 2008, 2009). The linear extrapolation method will be used for analysis of the structural progression endpoint (van der Heijde mTSS), including bone erosion scores and joint space narrowing, to impute missing data at time points when analyses are conducted (including the analyses at Week 24 and Week 52). For patients who discontinue from the study or for patients who miss a radiograph for any reason, baseline data and the most recent radiographic data prior to discontinuation or prior to the missed radiograph, adjusted for time, will be used for linear extrapolation to impute missing data at subsequent scheduled time points, including the primary analysis at Week 24. For patients who receive rescue therapy starting at Week 16 or at any time point thereafter, baseline data and the most recent radiographic data prior to initiation of rescue therapy, adjusted for time, will be used for linear extrapolation. For patients who discontinue from the study or permanently discontinue the study treatment after receiving rescue therapy, the radiographic data collected prior to initiation of rescue therapy should supersede the data collected before discontinuation.

All patients originally randomized to placebo will be switched to active treatment at Week 24; thus, there will be no observed data for the placebo arm after Week 24. Therefore, baseline data and the most recent radiographic data prior to initiation of the new therapy, adjusted for time, will be used for linear extrapolation at Week 52. Missing postbaseline values will be imputed only if both a baseline value and a postbaseline value from another time point are available, as long as the patient was receiving the same treatment at each applicable time point. Missing postbaseline values will not be imputed using postbaseline data from later time points.

For example:

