- (1) For a baricitinib-treated patient who did not require rescue therapy:
 - Missing data at Week 16 will be extrapolated from baseline and an early discontinuation visit prior to Week 16, if available.
 - Missing data at Week 24 will be extrapolated from baseline and the last available postbaseline value prior to Week 24.
 - Missing data at Week 52 will be extrapolated from baseline and the last available postbaseline value prior to Week 52, if available.
- (2) For a baricitinib- or placebo-treated patient who was rescued at Week 16:
 - Missing data at Weeks 24 or 52 will be extrapolated from baseline and Week 16.
- (3) For a placebo-treated patient who did not require rescue therapy:
 - Missing data at Week 16 will be extrapolated from baseline and an early discontinuation visit prior to Week 16, if available.

- Missing data at Week 24 will be extrapolated from baseline and the last available postbaseline value prior to Week 24.
- Missing data at Week 52 will be extrapolated from baseline and the last available postbaseline value at or prior to Week 24.

2. Other method: Last observation carried forward

A last-observation-carried-forward (LOCF) approach will also be used for the Week 24 analyses of mTSS, bone erosion scores, and joint space narrowing. Data observed at Week 24 will be analyzed according to randomized treatment group regardless of rescue status. Patients with missing data at Week 24, as a result of study discontinuation or unreadable x-rays, will have their data imputed by last postbaseline observation carried forward.

Details of the missing data imputation rules, methods for between-reader adjudication, score derivations, and other details for the bone erosion scores, joint space narrowing scores, and mTSS are provided in [Appendix 2](#) (van der Heijde Modified Total Sharp Score) and [Appendix 4](#).

[Table 6-1](#) summarizes the imputation techniques for the various endpoints.

Table 6-1 **Imputation Techniques for Various Efficacy and Safety Variables**

Endpoint	Imputation Method
ACR 20/50/70 responses, DAS28-hsCRP and DAS28-ESR LDA and remission, EULAR response criteria based on the 28-joint DAS, ACR/EULAR remission according to the Boolean-based definition, HAQ-DI improvement from baseline ≥ 0.22 and ≥ 0.3 , CDAI LDA and remission, and SDAI LDA and remission	NRI
JSN, bone erosion scores, and mTSS	Linear extrapolation method and LOCF
mTSS ≤ 0 , mTSS ≤ 0.5 , and mTSS \leq SDC	NRI
HAQ-DI, DAS28-hsCRP	mBOCF/mLOCF

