6.11. Efficacy Analyses

Efficacy analyses will use the mITT population defined in Section 6.1.3 and will generally be analyzed according to the following 2 formats:

- Week 0 (Visit 2) to Week 52 (Visit 15) with data included up to the time of rescue/switch. Formal statistical tests will be used to compare the baricitinib group to the placebo group for these efficacy outcomes through Week 24;
- Week 0 (Visit 2) to Week 52 (Visit 15) for rescued/switched patients with data included after rescue/switch. These efficacy results will be summarized by treatment group, but no formal statistical comparisons will be performed.

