6.16. Exploratory Analysis

- Comparison between baricitinib and placebo in change from baseline to Weeks 16, 24, and 52 in mTSS: The actual scores and change from baseline scores at Week 16, 24, and 52 in mTSS will be summarized. An ANCOVA model with baseline score, country/region, baseline joint erosion status, and treatment group in the model will be used to test the treatment difference between baricitinib and placebo in change from baseline to Week 24 in mTSS scores. Type III sums of squares for the LS means will be used for the statistical comparison; 95% CI will also be reported. The LS mean difference, SE, CI, and p-value will be presented. The linear extrapolation method described in Section 6.3 will be used. The LOCF approach described in Section 6.3 will be used as a sensitivity approach to the linear extrapolation method to impute missing data.

Supportive analyses using the cumulative responder curves, in which patients who have discontinued their randomized treatment are defined as progressors across the spectrum of choices of analysis thresholds will be provided.

- Descriptive statistics for the proportion of patients with mTSS change ≤ 0 by treatment group at Weeks 16, 24, and 52 will be provided by visit and treatment group. Logistic regression will be conducted to analyze the proportion of patients with mTSS change ≤ 0 at Weeks 16, 24, and 52 between baricitinib and placebo. The model for the logistic regression will consist of county/region, baseline joint erosion status, and treatment as fixed effects. Summaries by treatment group will be provided for the proportion of patients who improved or experienced no change (mTSS ≤ 0), or worsened (mTSS > 0).

In addition, the proportion of patients with change in mTSS $\leq SDC$ and mTSS ≤ 0.5 at Weeks 16, 24, and 52 will be analyzed in a similar manner as described for mTSS change ≤ 0 . The SDCs at Weeks 16, 24, and 52 are defined as the smallest detectable change which is

computed from the variability in Week 0 to Week 16, Week 24, or Week 52 change in scores assigned by the blinded imaging assessors, respectively (Bruynesteyn 2005).

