The linear extrapolation method described in Section 6.3 will be used to impute missing data. The categorical analyses described above will be applied to the mITT population, and a subset of mITT population that includes all randomized patients who received at least 1 dose of study drug, have non-missing baseline and at least 1 non-missing postbaseline mTSS measurement.

- Descriptive statistics for the actual score and change from baseline scores at Week 16, Week 24, and Week 52 in joint space narrowing and in bone erosion scores will be provided by visit and treatment group.
- Descriptive statistics for the proportion of patients achieving ACR20, ACR50, and ACR70 at each postbaseline visit through Visit 15 (Week 52) will be provided by visit and treatment group. A logistic regression with the same model specification as the primary analysis will be used for the treatment comparisons through Week 24 for ACR20, ACR50, and ACR70. The observed (“as-is”) values of the ACR20, ACR50, and ACR70 will be summarized as a sensitivity approach to the primary method of NRI. Using the “as-is” approach, the ACR values are calculated without applying any imputation to the components.
- Descriptive statistics for the proportion of patients achieving EULAR Responder Index based on the 28-joint count at each postbaseline visit will be provided by visit and treatment group. EULAR nonresponders and responders (moderate + good responders) will be summarized. The NRI method will be used as the missing data imputation technique. A logistic regression analysis will be performed to compare the proportion of EULAR responders between baricitinib and placebo through Week 24. The model will consist of country/region, baseline joint erosion status, and treatment as fixed effects. The analysis will be repeated to compare the treatment groups in proportion of patients achieving good responses. Apart from the aforementioned categories, a summary table with frequencies and percentages will be presented for the patients categorized as good responder, moderate responder, and nonresponder. The observed values will be analyzed as a sensitivity approach to the primary method that utilizes NRI.

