- A logistic regression analysis will be conducted to analyze the patients with specified categories up to Week 24 as below. The model for the logistic regression will consist of country/region, baseline joint erosion status, and treatment as fixed effects to compare baricitinib to placebo. Besides, descriptive statistics will be provided by visit and by treatment group for the following endpoints.
 - The proportion of patients achieving DAS28-ESR ≤ 3.2 and < 2.6 and DAS28-hsCRP ≤ 3.2 and < 2.6 at post-baseline visits.
 - The proportion of patients achieving HAQ-DI improvement from baseline ≥ 0.22 and ≥ 0.3
 - The proportion of patients achieving SDAI score ≤ 3.3 (ACR/EULAR remission index-based definition) and CDAI score ≤ 2.8 up to Week 52; the proportion of patients achieving CDAI score ≤ 10 and proportion of patients achieving SDAI score ≤ 11 up to Week 52.
 - The proportion of patients achieving ACR/EULAR remission according to the Boolean-based definition by treatment group.

- Change from baseline to postbaseline visits up to Week 24 in specific endpoints will be analyzed using an ANCOVA model with treatment, country/region, baseline joint erosion status, and baseline score in the model to test the treatment difference between baricitinib and placebo.
Besides, descriptive statistics will be provided by visit and by treatment group for the following endpoints. The mLOCF approach described in Section 6.3.1 will be used to impute missing data.
 - The percent change from baseline and change from baseline in individual components of the ACR core set, including TJC68, SJC66, patient's assessment of arthritis pain, Patient's Global Assessment of Disease Activity, Physician's Global Assessment of Disease Activity, and hsCRP at postbaseline visits.
 - The actual score and the change in DAS28-hsCRP and in DAS28-ESR from baseline to post-baseline visits.
 - The actual score and the change in HAQ-DI from baseline to post-baseline visits.
 - The actual score and the change in CDAI and in SDAI from baseline to post-baseline.

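### The Week 52 mTSS responder tests compare mostly observed baricitinib values with wholly extrapolated placebo values, and SAP Table 6-1 and SAP 6.16 name different imputation rules for the same three endpoints

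*SAP*

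**What the plan says.** SAP 6.16 plans logistic regression for mTSS change ≤0 "at Weeks 16, 24, and 52 between baricitinib and placebo", and handles ≤SDC and ≤0.5 in the same way. The analyses are run in the mITT population and in the subset with a baseline and at least one postbaseline mTSS value.

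On placebo data after the switch, SAP 6.3.2 says: "thus, there will be no observed data for the placebo arm after Week 24". For a placebo patient not rescued, "Missing data at Week 52 will be extrapolated from baseline and the last available postbaseline value at or prior to Week 24"; for a patient rescued at Week 16, in either arm, the Week 52 value comes from baseline and Week 16. SAP 6.1.4 fixes the time scale: "Any linear extrapolation will be based on the date of the x-ray set".

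Elsewhere formal testing generally stops at Week 24. SAP 6.11 states: "Formal statistical tests will be used to compare the baricitinib group to the placebo group for these efficacy outcomes through Week 24". Within 6.16, the continuous mTSS model is "used to test the treatment difference between baricitinib and placebo in change from baseline to Week 24 in mTSS scores", the ACR model "will be used for the treatment comparisons through Week 24 for ACR20, ACR50, and ACR70", and the lead-in to the other responder endpoints reads "A logistic regression analysis will be conducted to analyze the patients with specified categories up to Week 24 as below".

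On missing data, Table 6-1 lists NRI for mTSS ≤0, ≤0.5 and ≤SDC. The 6.16 text on the same endpoints names linear extrapolation.

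**The concern.** A Week 52 p-value here compares mostly observed baricitinib values with placebo values that are all projections. For ≤0.5 the projection interacts with the half-point scale, so the smallest positive change on placebo can never pass while the same observed change on baricitinib does. SAP 6.16 gives no reason for testing at Week 52 when the continuous mTSS comparison beside it is tested at Week 24.

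The imputation conflict is a second, independent problem. Under NRI a rescued or discontinued patient, or one without a film, fails the threshold. Under extrapolation the same patient may pass. Two programmers following the SAP could report different Week 24 results.

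**Working it through.** **Stated figures.** The plan gives none for the mTSS responder analyses. Its one design figure, 99% power for ACR20 at 60% v 35% with 144 per arm, reproduces and is unaffected: se0 = √(2 × 0.475 × 0.525/144) = 0.0589; se1 = √((0.24 + 0.2275)/144) = 0.0570; (0.25 − 1.96 × 0.0589)/0.0570 ≈ 2.36; power 0.991.

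**1. Observed changes lie on a 0.5 grid.** Erosion and joint-space grades are whole numbers (SAP Appendix 2). A joint missing at baseline is dropped throughout; one missing later takes its last score; nothing is prorated (Appendix 4). The change is the mean of two readers, also after adjudication. The grid is derived from these rules; the SAP does not state it.

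**2. Extrapolation factor** = (days from baseline film to Week 52) / (days from baseline film to last usable film).
- Nominal days (protocol Attachment 1): 365/168 = 2.17 from Week 24; 365/112 = 3.26 from Week 16.
- Allowed dates: a film may fall 14 days before to 30 days after its visit (SAP 6.1.4), and visits carry ±3 days, so the Week 24 film lies on Days 151–201 and the Week 16 film on Days 95–145. The baseline film is taken as 0–70 days before Day 0.
- Range from Week 24: 435/271 = 1.61 to 365/151 = 2.42. From Week 16: 435/215 = 2.02 to 365/95 = 3.84. With Week 52 at Day 360 the minimum is 430/271 = 1.59.

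**3. Effect on each threshold (placebo, Week 52).**
- ≤0.5: a change of 0.5 becomes 1.09 (Week 24 film) or 1.63 (Week 16 film), and at least 0.5 × 1.59 = 0.79. Enumerating baseline films 0–70 days before Day 0, last films on Days 20–201, Week 52 on Days 360, 365 and 370, and changes from −20 to +40 in steps of 0.5 gave no case where extrapolated ≤0.5 differed from last change ≤0.
- ≤0: the sign cannot change, so status is frozen at the last film before switch or rescue.
- ≤SDC: the last change must be at most 168/365 = 0.46 × SDC (Week 24 film) or 112/365 = 0.31 × SDC (Week 16 film). The documents give no SDC value.

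**4. Illustration under no drug effect (all inputs assumed).** Same progression in both arms; half the patients do not progress, half have an exponential annual slope with mean 2; SD of the two-reader mean change 0.8; rescue 15% in each arm, independent of progression; 144 per arm; unadjusted two-proportion test.

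| Threshold | Placebo | Baricitinib | Gap |
|---|---|---|---|
| ≤0.5 | 46.6% | 55.2% | 8.6 points to baricitinib; true null rejected about 31% |
| ≤0 | 46.6% (identical, by step 3) | about 5 points lower | about 5 points to placebo |

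For ≤0.5:
- With 43/288 = 14.9% baricitinib dropout (from the planned 245 completers) the gap is 7.0–7.6 points, rejection 22–25%.
- Over 18 scenarios with half not progressing, with and without that dropout, it is 3.8–14.0 points.
- If progression stops at Week 24 (middle case) it is 13–16 points.
- If every patient progresses, with dropout, it is +3.1, 0.0 and −1.1 points for mean slopes 1, 2 and 4.

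**5. The rule conflict at Week 24.** Let r be the rescue rate and s the share of rescued patients whose extrapolated change meets the threshold (p placebo, b baricitinib). Moving from extrapolation to NRI shifts the baricitinib-minus-placebo difference by r_p × s_p − r_b × s_b, plus a like term for discontinued patients and missed films. Assumed examples:
- Equal shares of 30–70% and a rescue gap of 5–20 points: 0.05 × 0.30 = 1.5 points to 0.20 × 0.70 = 14 points.
- Equal rescue of 15%, shares 50% placebo and 70% baricitinib: 0.15 × 0.50 − 0.15 × 0.70 = −3 points.

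**6. The rule conflict at Week 52.** SAP 6.3.1 makes patients without data at a visit nonresponders, and SAP 6.1 excludes placebo data after the switch. Literal NRI therefore puts every placebo patient at nonresponse. With under 5 responders in a category, SAP 6.1 replaces the logistic model with the Fisher test. The 6.3.1 sentence on rescued placebo patients stops at Week 24 and does not settle this.

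**The case against.** The strongest defence is that this is disclosed design. Protocol 12.2.1 foresees a structural comparison after Week 24 and prescribes extrapolation for it; protocol 6.3 lists mTSS change ≤0 at Week 52 as an exploratory objective. The cut is nominally 0.5 in both arms, and the placebo value is a projection under an openly stated linear assumption. That supports a descriptive Week 52 table. It does not make the p-value interpretable.

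A reader might infer that the Week 52 tests are biased towards baricitinib. The documents do not support that. The extrapolation can only remove placebo ≤0.5 responders relative to the last pre-switch film, but relative to true Week 52 status it also keeps as responders placebo patients at 0 who would have progressed later. In the same assumed case ≤0 leans the other way, and the ≤0.5 gap vanishes if everyone progresses. Nor do ≤0 and ≤SDC collapse as ≤0.5 does.

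A reader might also infer that these are the only possible Week 52 tests. That is not certain: the FACIT-F MCID regression is optional and carries no explicit Week 24 limit, and the SDAI and CDAI items mention Week 52 under a Week 24 lead-in.

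Rescued, discontinued or missing-film baricitinib patients are extrapolated too, so the asymmetry comes from baricitinib patients with an observed Week 52 film. The cumulative responder curves in 6.16 are a useful supportive view but do not replace the tests.

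On the rule conflict, the natural reading is to extrapolate first and apply NRI to what remains, since the mITT version needs some rule for patients who cannot be extrapolated. The SAP does not say so, and that reading sets aside the 6.3.1 rule that rescued patients are nonresponders.

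**Conclusion.** The concern holds for the planned Week 52 p-values and for the contradiction between Table 6-1 and 6.16. The identity of placebo ≤0.5 with ≤0 at the last usable film follows from the scoring rules and the allowed film dates. The percentage-point gaps and rejection rates do not: they rest on assumed progression, reader error, rescue and dropout, and neither their size nor their direction is fixed. The Week 24 shift between the two imputation rules is likewise unknown, and equal rescue rates do not make it zero. The endpoints are exploratory. This should be corrected, but nothing in the primary or secondary analyses depends on it.

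**What to change.** In SAP 6.16, limit the logistic regressions for mTSS change ≤0, ≤0.5 and ≤SDC to Weeks 16 and 24. Report Week 52 descriptively, with the placebo column labelled as extrapolated.

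In Table 6-1 and in the imputation sentence of 6.16, state one rule: linear extrapolation per 6.3.2 first, then NRI for mITT patients whose value at that visit is still missing. This also covers a patient with a Week 24 film but no Week 16 film, since 6.3.2 bars imputation from later films. Say explicitly that, for these endpoints, rescued patients are then extrapolated and not set to nonresponse. Record the change and its reason in the SAP and clinical study report, as protocol 12.2.1 requires.

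The cost is wording, the recorded justification and six exploratory Week 52 p-values (three endpoints × two populations). One limitation remains: at Week 24 a rescued patient's 0.5 becomes 0.5 × 24/16 = 0.75 and fails ≤0.5, in both arms.

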6.16.1.1. Analysis of Patient-Reported Outcomes Non-Diary Data

Observed patient-reported outcomes in duration of morning joint stiffness, Worst Tiredness NRS, and Worst Joint Pain NRS assessed using an electronic patient-reported outcomes (ePRO) tablet by visit and ePRO change from baseline values at Weeks 12, 24, and 52 will be summarized in listings.

The effect of baricitinib compared to placebo from baseline up to Week 24 and to Week 52 in terms of descriptive summaries with regard to PROs will be evaluated by the following measures:

- **Duration of Morning Joint Stiffness**

The duration of morning joint stiffness is a patient-administered item that allows for the patients to enter the length of time in minutes that their morning joint stiffness lasted on the day prior to that visit using an ePRO tablet. Durations recorded as longer than 12 hours (720 minutes) will be truncated to 720 minutes for analysis.

Duration of morning joint stiffness will be measured at baseline and at postbaseline visits. Summary statistics of the actual score and change from baseline will be displayed by treatment and protocol-specified visit.

The comparison between baricitinib and placebo in change from baseline through Week 24 in duration of morning joint stiffness will be analyzed using a nonparametric method involving the Hodges-Lehmann estimator. For the comparison between baricitinib and placebo, the median difference of change from baseline score and its 95% CI from the Hodges-Lehmann estimator will be presented. The p-value for the median difference of

change from baseline will be calculated using the Wilcoxon rank-sum test. A 95% CI for the median change from baseline score within each treatment group will be calculated using distribution-free confidence limits. The mLOCF approach will be used to impute missing data. The observed values may be analyzed as a sensitivity approach to the primary method that utilizes mLOCF.

- **Tiredness Severity Numeric Rating Scale (Worst Tiredness NRS)**

The Worst Tiredness NRS is a patient-administered, single-item, 11-point horizontal scale anchored at 0 and 10, with 0 representing “no tiredness” and 10 representing “as bad as you can imagine.” Patients rate their tiredness by selecting the 1 number that describes their worst level of tiredness during the past 24 hours using an ePRO tablet.

Worst Tiredness NRS will be measured at baseline and at postbaseline visits. Summary statistics of the actual score and change from baseline will be displayed by treatment and protocol-specified visit.

The change from baseline in Worst Tiredness NRS to Week 24 will be analyzed using ANCOVA. The ANCOVA model will consider treatment, country/region, and baseline joint erosion status as fixed effects and baseline score as a covariate with change from baseline being the dependent variable. To test the treatment difference between baricitinib and placebo, the LS mean difference, 95% CI, and p-value will be presented. The mLOCF approach will be used to impute missing data. The observed values may be analyzed as a sensitivity approach to the primary method that utilizes mLOCF.

- **Severity of Joint Pain Numeric Rating Scale (Worst Joint Pain NRS)**

The Worst Joint Pain NRS is a patient-administered, single-item, 11-point horizontal scale anchored at 0 and 10, with 0 representing “no pain” and 10 representing “pain as bad as you can imagine.” Patients rate their pain by selecting the 1 number that describes their worst level of pain during the past 24 hours using an ePRO tablet.

Worst Joint Pain NRS will be measured at baseline and at postbaseline visits. Summary statistics of the actual score and change from baseline will be displayed by treatment and protocol specified visit.

The change from baseline in Worst Joint Pain NRS to Week 24 will be analyzed using ANCOVA. The ANCOVA model will consider treatment, country/region, and baseline joint erosion status as fixed effects and baseline score as a covariate with change from baseline being the dependent variable. To test the treatment difference between baricitinib and placebo, the LS mean difference, 95% CI, and p-value will be presented. The mLOCF approach will be used to impute missing data. The observed values may be analyzed as a sensitivity approach to the primary method that utilizes mLOCF.

- **FACIT-F**

The FACIT-F scale (Cella and Webster 1997) is a 13-item, symptom-specific questionnaire that specifically assesses the self-reported severity of fatigue and its impact upon daily activities and functioning. The FACIT-F uses 0 (“not at all”) to 4 (“very much”) numeric rating scales to assess fatigue and its impact in the past 7 days. Scores range from 0 to 52 with higher scores indicating more fatigue.

FACIT-F scores will be measured at baseline and at postbaseline visits.

Summary statistics of the actual score and change from baseline will be displayed by treatment and protocol-specified visit.

The change from baseline in FACIT-F score to Week 24 will be analyzed using ANCOVA. The ANCOVA model will consider treatment, country/region, and baseline joint erosion status as fixed effects and baseline score as a covariate with change from baseline being the dependent variable. To test the treatment difference between baricitinib and placebo, the LS mean difference, 95% CI, and p-value will be presented. The mLOCF approach will be used to impute missing data.

The Minimum Clinically Important Difference (MCID) for the FACIT-F score is defined as ≥ 3.56 improvement (increase) from the baseline value of the Fatigue Subscale Score. The summary and analysis of the FACIT-F score will include the number and percent of patients achieving MCID at each postbaseline visit. The proportion of patients achieving the FACIT-F score MCID may also be analyzed using a logistic regression model with treatment, country/region, and baseline joint erosion status as fixed effects. The p-value and 95% CI of the odds ratio from the logistic regression model will be reported. The 95% CI of MCID rate difference will be calculated using the Newcombe-Wilson method without continuity correction. The NRI method described in Section 6.3.1 will be used to impute missing data.

- **WPAI-RA**

The WPAI-RA questionnaire was developed to measure the effect of general health and symptom severity on work productivity and regular activities in the last 7 days of the visit. It contains 6 items covering overall work productivity (health), overall work productivity (symptom), impairment of regular activities (health), and impairment of regular activities (symptom). Scores are calculated as impairment percentages (Reilly et al. 1993).

The WPAI-RA yields 4 types of scores:

- Absenteeism (work time missed)
- Presenteeism (impairment at work/reduced on-the-job effectiveness)
- Work productivity loss (overall work impairment/absenteeism plus presenteeism)
- Activity Impairment

Six questions will be answered:

- Q1 = currently employed
- Q2 = hours missed due to specified problem
- Q3 = hours missed due to other reasons
- Q4 = hours actually worked
- Q5 = degree that RA affected productivity while working
- Q6 = degree that RA affected regular activities

WPAI-RA outcomes are expressed as impairment percentages, with higher numbers indicating greater impairment and less productivity, ie, worse outcomes, as follows:

- Percentage work time missed due to RA “absenteeism”: $Q2/(Q2+Q4)$

- Percentage impairment while working due to RA “presenteeism”: Q5/10
- Percentage overall work impairment due to RA “work productivity loss”: $Q2/(Q2+Q4)+[(1-Q2/(Q2+Q4))x(Q5/10)]$
- Percentage activity impairment due to RA “activity impairment”: Q6/10
- Multiply scores by 100 to express in percents.

WPAI-RA scores will be measured at baseline and at postbaseline visits.

The proportion of patients who were employed versus not employed at baseline will be summarized, along with by-visit summaries of changes in employment status (i.e. proportion of patients employed at baseline who are still employed at the postbaseline visit and the proportion of patients not employed at baseline who remained unemployed at the postbaseline visit). The analyses of absenteeism, presenteeism, and work productivity loss will be based on patients employed at both baseline and postbaseline visits. The analysis of activity impairment will be based on the mITT population. Summary statistics of the actual and change from baseline scores based on absenteeism, presenteeism, work productivity loss, and activity impairment will be displayed by treatment and protocol-specified visit.

The change from baseline in each of the 4 types of scores of WPAI-RA (absenteeism, presenteeism, work productivity loss, and activity impairment) to Week 24 may be analyzed using ANCOVA. The ANCOVA model will consider treatment, country/region, and baseline joint erosion status as independent fixed effects and the baseline score as a covariate with change from baseline being the dependent variable. To test the treatment difference between baricitinib and placebo, the LS mean difference, 95% CI, and p-value will be presented.

- **European Quality of Life–5 Dimensions–5 Level (EQ-5D-5L)**

The EQ-5D-5L is a standardized measure of health status of the patient at the visit (same day) that provides a simple, generic measure of health for clinical and economic appraisal. The EQ-5D-5L consists of 2 components: a descriptive system of the respondent’s health and a rating of his or her current health state using a 0- to 100-mm VAS. The descriptive system comprises the following 5 dimensions: mobility, self-care, usual activities, pain/discomfort, and anxiety/depression. Each dimension has 5 levels: no problems, slight problems, moderate problems, severe problems, and extreme problems. The respondent is asked to indicate his/her health state by ticking (or placing a cross) in the box associated with the most appropriate statement in each of the 5 dimensions. It should be noted that the numerals 1 to 5 have no arithmetic properties and should not be used as a cardinal score. The VAS records the respondent’s self-rated health on a vertical VAS in which the endpoints are labeled “best imaginable health state” and “worst imaginable health state.” This information can be used as a quantitative measure of health outcome. The EQ-5D-5L health states, defined by the EQ-5D-5L descriptive system, may be converted into a single summary index by applying a formula that essentially attaches a value (also called weights) to each of the levels in each dimension (Brooks 1996; EuroQol Group 2011 [WWW]; Herdman et al. 2011).

The EQ-5D-5L questionnaire is completed by the patient in this study at baseline and post-baseline visits up to Week 52 (Visit 15). The EQ-5D-5L will be scored according to the

developer's instructions (scoring guidelines). Three outcomes are described for each treatment group by visit according to the following:

- A health profile: summary statistics will be provided, including number of patients and proportions of categorical responses for the 5 dimensions (mobility, self-care, usual activity, pain/discomfort, and anxiety/depression)
- A health state index score: the UK algorithm (Szende et al. 2006) will be used to produce a patient-level index score between -0.59 and 1.0 (continuous variable); the same will be done using the US algorithm which produces a patient-level index score between -0.11 and 1.0.
- A self-perceived current health score: calculated from patient level EQ VAS responses (continuous variable).

The change in health state index scores and EQ VAS score from baseline through Week 24 (Visit 11) may be analyzed using an ANCOVA model with the following terms: treatment, country/region, baseline joint erosion status, and baseline score. Within each treatment arm, the LS mean, SE of the LS mean, and p-value will be reported. The LS mean difference between baricitinib and placebo, 95% CI for the mean difference, and p-value will be reported. ANCOVA will be conducted after imputing the postbaseline missing values using mLOCF.

All the aforementioned health outcome analyses will be performed on the mITT population. Descriptive statistics will be provided for all the parameters by visit and treatment group for baseline and all postbaseline visits.

- **Healthcare Resource Utilization**

The healthcare resource utilization data will be collected by site staff regarding the number of visits to medical care providers such as general practitioners, specialists, physical or occupational therapists, and other non-physical care providers for services outside of the clinical study; emergency room admissions; hospital admissions; and concomitant medications related to the treatment of RA. These data will be collected to support economic evaluations of treatment. A summary table including the following will be presented for the period of the past 2 months prior to study treatment as baseline and summarized at baseline and at post-baseline intervals (Week 0 to Week 12, Week 0 to Week 24, Week 24 to Week 52, and Week 0 to Week 52).

Healthcare resource utilization – Healthcare providers:

A summary of the number of consultations of medical care providers for care/treatment of RA will be provided for the period of the past 2 months prior to the study treatment. It will also be summarized at the post-baseline intervals described earlier. The number of consultations will be totaled by days and patients for the categories:

- Healthcare Provider Consultation
- Emergency Room Consultation

The "Healthcare Provider Consultation" comprises the following:

- General Practitioner (Such as family doctor or primary care physician)
- Specialist

- Rheumatologist
- Occupational Therapist
- Physical therapist
- Non-physician care providers

For the “Emergency Room Consultation” every necessary Emergency Room (ER) or equivalent facility consultation will be counted.

Healthcare resource utilization – Inpatient Hospitalization:

A summary table including the following will be presented from the period of the past 2 months prior to study treatment and at post-baseline intervals for the following details:

- Frequency of patient’s hospitalization and need for staying overnight because of their RA.
- Frequency of hospitalization type (general ward/intensive care ward).
- Descriptive statistics for the total number of days in hospital.

Healthcare resource utilization – Work Status:

A frequency table for the non-missing statements on work status for the period of the past 2 months prior to study treatment and at post-baseline intervals will be provided for the following details:

- Working for pay full-time (>36 hours per week)
- Working for pay part-time (≤ 36 hours per week)
- Unemployed, unrelated to study disease disability
- Unemployed due to study disease disability
- Other [Keeping house (full-time), Student (full-time), Student (part-time), Retired, Volunteer work]

